2.2 Secondary Objectives (or Aim)

The secondary objective is to evaluate preliminary efficacy of DECIDES using a randomized trial.

Hyp 2a. AYA randomized to DECIDES and DECIDES + coach will report greater involvement in and shared decision-making than AYA assigned to Usual Care.

Hyp 2b. AYA and caregiver(s) randomized to DECIDES and DECIDES + coach will report more positive decision-making processes (greater knowledge of their cancer and clinical trials, more balanced attitudes toward clinical trials, and more decision certainty, satisfaction and self-efficacy) compared with those assigned to Usual Care.

Hyp 2c. For DECIDES and DECIDES + coach participants who are offered enrollment on a clinical trial, the enrollment decision (yes/no) will align with AYA values.

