3.1.3 Assessment Time Points

All AYA and caregiver(s) that enroll to participate in the study will complete an electronic baseline assessment at time of enrollment (prior to randomization) and again at post-intervention (i.e., approximately six-weeks after date of randomization). Additionally, AYA and caregiver(s) randomized to DECIDES or DECIDES + coach will also complete an audio or video-recorded semi-structured qualitative interview with a member of the study team via Microsoft Teams after the post-intervention assessment.

Oncology health care providers of enrolled AYA and caregiver(s) will be invited to preview the DECIDES website, participate in an electronic rating scale and complete an audio-recorded semi-structured qualitative interview with a member of the study team via Microsoft Teams.

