5.2 Self-Report Measures

Demographics: Variables will be collected based on AYA and caregiver(s) self-report and review of the patients' electronic health record. Demographic variables include age, gender, race/ethnicity, education/work, health care, and family history.

Intensity of Treatment Rating Scale (ITR-3): The revised version of a reliable and valid method for classifying pediatric oncology treatment protocols. This scale, completed by a medical provider, categorizes the intensity of pediatric cancer treatment from least through most intensive based on treatment modality and stage/risk level for the patient. ⁽⁹⁹⁾

Acceptability of the Decision Aid: A study-team developed measure used to obtain acceptability ratings from AYA and caregiver(s) (assigned to DECIDES or DECIDES + coach only). This measure is based on The Ottawa Hospital's measure of acceptability ratings regarding comprehensibility of components of a decision aid, its length, pace, amount of information, balance in presentation of information about options, and overall suitability for decision making. ⁽⁶⁾

Systems Usability Scale (SUS): This is a cost-effective, 10-item scale that is widely used to obtain a reference score for participants' view of a product's usability. This scale includes 10 statements that are scored on a 5-point scale of strength of agreement. Final scores can range from 0 to 100, in which higher scores indicate better usability. AYA and caregiver(s) (assigned to DECIDES or DECIDES + coach only) and oncology health care providers will complete this scale. ^(36,71)

Control Preferences: This scale assesses patient decision-making preferences and roles (i.e., patient's preferred role [baseline] versus the role they actually played in making a treatment decision [post-intervention]). This scale has been adapted for use in this study to assess caregiver decision-making preferences and roles, as well (i.e., caregiver's preferred role of patient [baseline] versus the role the patient actually played in making a treatment decision [post-intervention]). Decision-making preferences and roles are evaluated using three categories: 1) patient led, 2) shared, or 3) oncologist/caregiver led. ^(74,75)

Physician Decision Making Scale: A 5-item scale that measures physician involvement in medical decision-making. Items are rated on a 3-point scale ranging from 1 ("Yes, definitely") to 3 ("No"). Higher scores reflect lower involvement in decision-making. ⁽¹⁰⁰⁾

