5.3 Semi-Structured Qualitative Interview

A semi-structured, qualitative interview guide designed by the study team for use with AYA and caregiver(s) (assigned to DECIDES or DECIDES + coach), and oncology health care providers. The purpose of the interview is to obtain further information from participants about the process of treatment decision-making and their experience using DECIDES, the decision aid. Participants will be interviewed by a study team member via remote video conference software (Microsoft Teams). All interviews will be audio and/or video recorded and professionally transcribed (by a CHOP-approved vendor with a BAA in place), and the interview data will be analyzed.

Table 1. Measures

Construct	Measure	Administration	
		T1	T2
Demographics	Electronic Health Record; AYA/Caregiver Self-Report	AYA, CG	
Treatment Intensity	Intensity of Treatment Rating Scale (ITR-3) ⁽⁹⁹⁾	PR	
Acceptability ^(D)	Acceptability of the Decision Aid ⁽⁶⁾		AYA, CG
Usability ^(D)	The Systems Usability Scale ^(36,71)		AYA, CG, PR
AYA Involvement in Shared Decision-Making	Control Preferences ^(74,75)		AYA, CG
	Physician Decision-Making Scale ⁽¹⁰⁰⁾		AYA, CG
	Shared-Decision Making Questionnaire (SDM-Q-9) ⁽⁹⁴⁾		AYA, CG
Knowledge	AYA Hope Survey: Information Need ^(76,77)	AYA, CG	
	Knowledge of Clinical Trials ⁽⁶⁴⁾	AYA, CG	AYA, CG
Attitudes to Clinical Trials	Pediatric Research Participation Questionnaire	AYA, CG	AYA, CG
Alignment of Decision with Values	(PRPQ) ^(15,16)		AYA, CG
Decision-Making	Certainty	Decisional Conflict Scale ⁽⁶⁵⁾	AYA, CG
	Satisfaction	Satisfaction with Decision Scale ⁽⁶⁶⁾	AYA, CG
	Self-Efficacy	Decision Self-Efficacy Scale ⁽⁶⁷⁾	AYA, CG
	Regret	Decision Regret Scale ⁽⁷²⁾	AYA, CG
Health-Related Quality of Life	PROMIS Parent Proxy Profile-25 ⁽⁹⁸⁾	CG	CG
	PROMIS Pediatric Profile-25 ⁽⁹⁷⁾	AYA (15-17)	AYA (15-17)
	PROMIS-29 Profile ⁽⁹⁶⁾	AYA(18-24)	AYA(18-24)
*Distress	Distress Thermometer ⁽⁷³⁾	AYA, CG	AYA, CG
*Valence and Arousal	Affective Slider ⁽⁸⁷⁾	AYA, CG	
*Awareness of Feeling Emotions	Affective Orientation (AO15) ⁽⁸⁸⁾	AYA, CG	
*Developmental Status	Developmental Task Questionnaire ^(89,92)	AYA	
*Psychosocial Maturity	Consideration of Future Consequences ⁽⁹⁰⁾	AYA, CG	
	Psychosocial Maturity Inventory ⁽⁹⁵⁾	AYA	
	Emotion Regulation Questionnaire ⁽⁹¹⁾	AYA, CG	
*Problem-Solving	Family Assessment Device (FAD): Problem-Solving ⁽⁹³⁾	AYA, CG	
Semi-Structured Qualitative Interview ^(D)	DECIDES Interview Guide		AYA, CG, PR

* = Covariate

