(D) = measure for participants randomized to DECIDES or DECIDES + coach only

T1 = Pre-Intervention; T2 = Post-Intervention; AYA = Adolescent/Young Adult; CG = Caregiver; PR = Health Care Provider

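### Section 5.2 takes the Control Preferences preferred role at baseline but Table 1 schedules the scale at T2 only; and its three categories do not fit the section 6.2 t test

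*Combined protocol and SAP*

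**What the plan says.** **Timing in the text.** Section 5.2 describes the patient version of Control Preferences as the "preferred role [baseline] versus the role they actually played in making a treatment decision [post-intervention" measurement. It describes the adapted caregiver version as the "caregiver's preferred role of patient [baseline] versus the role the patient actually played in making a treatment decision [post-intervention" measurement. Both versions therefore need one item before the intervention and one after it.

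**Timing in the schedule.** Table 1 (printed under section 5.3) lists "Control Preferences" first under the construct of AYA involvement in shared decision-making. Its T1 cell is empty and its T2 cell names AYA and caregivers. The legend reads "T1 = Pre-Intervention; T2 = Post-Intervention".

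**What baseline means.** Under section 3.1.3, AYA and caregivers "will complete an electronic baseline assessment at time of enrollment (prior to randomization) and again at post-intervention". T1 is thus the only survey completed before randomization.

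**Scale and analysis.** Section 5.2 states: "Decision-making preferences and roles are evaluated using three categories: 1) patient led, 2) shared, or 3) oncologist/caregiver led". Section 6.2 says that all measures for Hyp 2a and Hyp 2b are continuous. On that ground it plans group means with 95% CIs and two-sample t tests on the post-intervention outcomes. Hyp 2a (section 2.2) is that AYA in the two DECIDES arms "will report greater involvement in and shared decision-making than AYA assigned to Usual Care".

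**The concern.** The text calls for two administrations of Control Preferences and the schedule provides one. A survey built from Table 1 would either never ask the preferred role or ask it at T2, about six weeks after randomization. By then the DECIDES arms have had access to a values exercise, and the participant may already have played a role in the decision. Either could shape the stated preference, so a T2 answer does not replace a baseline one, and a missed baseline item cannot be collected afterwards.

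The gap between preferred and actual role matters to this trial. The background section reports that AYA involvement in clinical trial decisions was more limited than they wanted, and Control Preferences is the only instrument in section 5.2 described as measuring that gap.

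The second problem concerns analysis. A mean and a t test need a score. Section 5.2 gives this scale three named categories and no scoring rule, so the planned analysis of one of the three Hyp 2a instruments is not defined.

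**Working it through.** The timing point rests on no sample-size or power figure, so the check is a comparison of passages.

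**1. Text against schedule**

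| Item | Section 5.2 | Table 1 |
|---|---|---|
| AYA: preferred role | baseline | not scheduled at T1 |
| AYA: actual role | post-intervention | T2 |
| Caregiver: preferred role of the patient | baseline | not scheduled at T1 |
| Caregiver: actual role of the patient | post-intervention | T2 |

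No other section schedules the preferred-role item at T1.

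**2. Could the empty cell be an artefact of reading the PDF?** Probably not. The Control Preferences row has the same pattern as the other T2-only rows (Acceptability, Systems Usability Scale, Physician Decision-Making Scale, SDM-Q-9). Rows given at both times, such as Knowledge of Clinical Trials and the Distress Thermometer, print the respondents twice. The visibly damaged parts are elsewhere: the Decision-Making block, which has an extra sub-column, and the PRPQ entry, which is split over two rows. The original table should still be checked.

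**3. What is lost if Table 1 is followed.** Preferred role before randomization: 0 of 50 evaluable families. Preferred-versus-actual comparison as section 5.2 describes it: cannot be formed.

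**4. What is not lost.** Section 6.2 compares groups on post-intervention outcomes only. The actual role, the SDM-Q-9 and the Physician Decision-Making Scale are all scheduled at T2 under the same construct, so Hyp 2a has its three instruments under either reading.

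**5. Scale against test.** The categories have a natural order of AYA involvement: patient led, shared, oncologist/caregiver led. That supports either a proportion (patient led or shared, against the third category) or an ordinal comparison. Neither needs the T1 item.

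**6. Precision of a proportion.** Inputs: 10 usual-care families and 20 per DECIDES arm (section 3.1). Assumption, not in the documents: a true proportion of 0.5 in each arm, which gives the widest interval. Normal approximation, a rough guide at this size:

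- Usual care alone: half-width = 1.96 × √(0.5 × 0.5 / 10) = 1.96 × 0.158 = 0.31.
- Usual care against one DECIDES arm: half-width = 1.96 × √(0.25/10 + 0.25/20) = 1.96 × 0.194 = 0.38.

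So a usual-care proportion is known to about ±31 percentage points, and a difference from one DECIDES arm to about ±38. This holds for the proportion with a patient-led or shared role and for the proportion whose actual role matches the preferred one.

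**The case against.** **The mismatch may be clerical.** Section 5.2 states the timing twice and separates the two items, whereas Table 1 gives the whole scale one row. An omission from the table is at least as plausible as a missing survey item. The documents do not show the REDCap build. This stands: the loss is conditional on the table being followed. The contradiction remains, and someone has to check the survey.

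**Hyp 2a is not damaged.** A reader might infer that Hyp 2a cannot be tested without the baseline item. The documents do not support that. Hyp 2a concerns greater involvement, section 6.2 uses post-intervention measures, and no section 6 analysis compares preferred with actual role. What is at risk is a measure that section 5.2 describes and section 6 never uses.

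**Agreement is not involvement.** It is tempting to make the match between preferred and actual role the replacement for the t test. That changes the question. An AYA who wanted a caregiver-led decision and got one counts as a match although involvement was low. One who became more involved than first preferred counts as a mismatch. Agreement can therefore run against Hyp 2a and belongs beside the main comparison, not in its place.

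**The baseline item is itself imperfect.** Section 3.3.1 allows enrollment up to six weeks after diagnosis or relapse and does not require that the treatment decision is still open. Some T1 preferences may follow the decision. This also stands, but a T1 answer still precedes randomization and cannot have been changed by DECIDES.

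**Conclusion.** The contradiction is real and worth correcting. Section 5.2 and Table 1 cannot both be followed. Under Table 1 no participant has a pre-randomization preferred role, and the preferred-versus-actual comparison in section 5.2 is lost for all 50 families. This assumes that the Control Preferences row was read correctly and that the survey follows the table; the documents do not settle the second. The Hyp 2a comparison of actual role at T2 survives in either case.

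The analysis point does not depend on the timing point. The section 6.2 premise that all measures are continuous is wrong for this three-category scale, and the t test should be replaced for it. Because the aim is preliminary efficacy and usual care has 10 families, neither the role proportion nor the agreement figure will be precise.

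**What to change.** 1. In Table 1, enter AYA and CG at T1 for the preferred-role item of Control Preferences, and keep the actual-role item at T2 for both. This brings the table into line with section 5.2.
2. Confirm that the REDCap T1 survey contains the preferred-role item in both the AYA and caregiver versions. If families have already completed T1 without it, record how many; do not fill the gap with a preference asked at T2.
3. In section 6.2, except Control Preferences from the continuous-measure statement. For Hyp 2a, compare by arm the proportion of AYA whose actual T2 role was patient led or shared, with a 95% CI. Use an exact test on that proportion or an ordinal test on the three categories, and name the choice before the data are examined.
4. Report agreement between T1 preferred and T2 actual role as a descriptive supplement by arm. Note that it is imprecise with 10 usual-care families and that some T1 preferences may follow the treatment decision.

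Cost: a table correction, a survey check, at most one short T1 item per respondent, and a few sentences in section 6.2. No change to sample size or visits is needed.

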Satisfaction with Decision Scale: This is a valid and reliable 6-item instrument that measures patient satisfaction with a health care decision. The scale provides an efficient measure to evaluate decision-assisting technologies or patient-provider interactions aimed at involving patients in decision-making. Higher scores indicate higher satisfaction with the decision that was made.⁽⁶⁶⁾

Decision Self-Efficacy Scale: This is a valid and reliable 11-item instrument that measures self-confidence in one's abilities in decision-making (including shared decision-making). Items are rated on a 5-point scale, ranging from "not at all confident" (0) to "very confident" (4). Higher scores indicate higher self-efficacy.⁽⁶⁷⁾

Decision Regret Scale: This is a valid and reliable 5-item instrument that measures distress or remorse after a (health care) decision. Items are rated on a 5-point scale, ranging from strongly agree (1) to strongly disagree (5). Items 2 and 4 are reverse coded so that for each item, a higher score will indicate more regret.⁽⁷²⁾

PROMIS Profile: 25, 29, and Parent-Proxy The PROMIS measures assesses physical function mobility, depressive symptoms, fatigue, peer relationships, pain intensity, and pain interference. The PROMIS Pediatric Profile (25 items) is intended for use with those under age 18; the PROMIS Profile (29 items) is intended for use with those over age 18; and the PROMIS-Parent Proxy Profile (25 items) is a parent-report measure.⁽⁹⁶⁻⁹⁸⁾

Distress Thermometer: The Distress Thermometer is from the National Comprehensive Cancer Network (NCCN) Practice Guidelines in Oncology for Distress Management. It is an illustration (thermometer) used with patients to rate the number that best describes how much distress they have been experiencing in the past week, ranging from "no distress" (0) to "extreme distress" (10).

Affective Slider (AS): This is a digital self-reporting tool composed of two slider controls for the quick assessment of arousal (top) and pleasure (bottom) on a continuous scale. The

AS does not require written instructions. The scale is intentionally displayed using a neutral chromatic palette to avoid bias in rating (due to emotional connotation of colors). ⁽⁸⁷⁾

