Affective Orientation (AO15): This is a valid and reliable 15-item measure used to assess how people use feelings and emotions to guide their behavior. Items are rated on a 5-point scale, ranging from strongly disagree (1) to strongly agree (5). Higher scores reflect greater awareness of emotions. ⁽⁸⁸⁾

Developmental Task Questionnaire (DTQ): The adolescent version of the DTQ is a 9-item self-report questionnaire that assesses adolescents' perceived developmental status; whereas the young adult version includes 8 items that assess developmental tasks for emerging adulthood. Items are rated on a 3-point scale ranging from "not yet started" (1) to "already developed" (3). Both adolescents and young adults are also asked to rank how important it is for them to achieve each of the normative developmental tasks on a 3-point scale, ranging from "not important" (1) to "very important" (3). ^(89,92)

Consideration of Future Consequences (CFC): This valid and reliable 12-item measure is used to assess the extent to which people consider distant versus immediate consequences of potential behaviors. Items are rated on a 5-point scale ranging from "extremely uncharacteristic" (1) to "extremely characteristic" (5). The CFC is scored so that higher numbers indicate a greater consideration of future consequences. ⁽⁹⁰⁾

Psychosocial Maturity Inventory (PMI): This is a 30-item self-report measure for AYA used to evaluate developmental aspects of maturity (i.e., self-reliance, self-concept, and work orientation). Items are rated on a 4-point scale, ranging from "agree strongly" (1) to "disagree strongly" (4). ⁽⁹⁵⁾

Emotion Regulation Questionnaire (ERQ): This is a valid and reliable 10-item measure used to assess processes of emotion regulation (cognitive reappraisal and expressive suppression). Items are rated on a 7-point scale ranging from "strongly disagree" (1) to "strongly agree" (7). The average score of items in the cognitive reappraisal subscale is calculated and the average score of items in the expressive suppression subscale is calculated. Higher scores indicate the greater use of that particular emotion regulation strategy, whereas lower scores indicate less frequent use. ⁽⁹¹⁾

Family Assessment Device (FAD): The Problem Solving subscale of the FAD includes 5 items that are rated on a 4-point scale ranging from "strongly agree" (1) to "strongly disagree" (4), with higher scores indicating more problematic functioning. ⁽⁹³⁾

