6 STATISTICAL CONSIDERATIONS

Demographic characteristics and all measurements will be summarized.

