6.2 Secondary Endpoints

The secondary objective is to evaluate preliminary efficacy of DECIDES using a randomized trial.

Hyp 2a and Hyp 2b. Because all measures are continuous, the primary analyses will be summarizing mean and 95% CI by groups and two-sample t test comparing groups for the post-intervention outcome measures. With the sample size of 20 family units for each DECIDES group and 10 family units for usual care, we will have 80% power to detect an effect size of 1.26 (that is, mean difference between the two groups is 1.26 x Standard Deviation).

Hyp 2c. Each AYA and caregiver will have two value scores: Σ factors endorsed as supporting enrollment/ Σ factors endorsed as not supporting enrollment. Consistency of value to enrollment decision will be evaluated with Tetrachoric correlation with 95% CI.

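### Decision self-efficacy probably has no baseline score and is compared by an unadjusted t test; 11 items at T1 plus a baseline-adjusted analysis would be a cheap gain in precision.

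*Combined protocol and SAP*

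**What the plan says.** Section 2.2 predicts that AYA and caregivers in the two DECIDES arms will report, among other things, "more decision certainty, satisfaction and self-efficacy) compared with those assigned to Usual Care".

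Section 5.2 describes the Decision Self-Efficacy Scale: "This is a valid and reliable 11-item instrument that measures self-confidence in" one's own decision-making. The same section ties satisfaction and regret to a decision already taken.

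Table 1 (section 5.3) has one administration entry for the "Decision Self-Efficacy Scale". It lists Knowledge of Clinical Trials and the PRPQ at both T1 and T2. It also stars a group of T1 scales as covariates: Distress Thermometer, Affective Slider, AO15, Developmental Task Questionnaire (DTQ), Consideration of Future Consequences (CFC), Psychosocial Maturity Inventory (PMI), Emotion Regulation Questionnaire (ERQ) and FAD Problem Solving.

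Section 6 opens with a general statement: "Demographic characteristics and all measurements will be summarized". For Hyp 2a and 2b, section 6.2 plans group means with 95% CIs and a "two-sample t test comparing groups for the post-intervention outcome measures". No baseline score or covariate is named. The power statement begins "With the sample size of 20 family units for each DECIDES group and 10 family units for usual care" and gives 80% power for 1.26 SD.

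**The concern.** Self-efficacy exists before a treatment decision does, so it can be measured before randomization. Knowledge and attitudes, two other Hyp 2b outcomes of that kind, do have a T1 score. Self-efficacy apparently does not, and no reason is given.

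Without a T1 score, a chance difference between arms at entry cannot be seen or adjusted for. With 10 and 20 families such differences are not rare: the standard error of a baseline mean difference is sqrt(1/10 + 1/20) = 0.39 SD, so a gap above 0.5 SD in either direction occurs about 20% of the time under sound randomization. Stratification is on age group only.

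At stake is how much the self-efficacy comparison can show with only 10 controls. A baseline not collected before randomization cannot be recovered afterwards.

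**Working it through.** **1. The plan's own figure.** Inputs from section 6.2: 10 vs 20 families, 80% power, 1.26 SD. The section states no alpha. By noncentral t with 28 df:
- two-sided 0.05: power at 1.26 SD is 88.1%; detectable effect 1.12 SD;
- two-sided 0.025 (for instance, a split over two comparisons with Usual Care): power at 1.26 SD is 80.6%; detectable effect 1.25 SD.

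The stated figure therefore fits 0.025. Both levels are carried forward.

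**2. Baseline score collected, analysis unchanged.** The t test uses T2 scores only, so the detectable effect does not move.

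**3. Baseline score used as a covariate.** The residual variance is multiplied by (1 − r²), where r is the T1-T2 correlation, and one df is lost (27). Then

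detectable effect = δ × sqrt(1 − r²) × sqrt(1/10 + 1/20),

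where sqrt(0.15) = 0.3873 and δ is the noncentrality that gives 80% power. At 0.05, δ = 2.902 (28 df) or 2.906 (27 df). At 0.025, δ = 3.230 or 3.235.

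Examples at 0.05: no covariate, 2.902 × 0.3873 = 1.124. With r = 0.5, 2.906 × 0.866 × 0.3873 = 0.975.

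| r (assumed) | Detectable, 0.05 | Power at 1.0 SD, 0.05 | Detectable, 0.025 |
|---|---|---|---|
| none (planned) | 1.124 | 70% | 1.251 |
| 0.3 | 1.074 | 74% | 1.195 |
| 0.5 | 0.975 | 82% | 1.085 |
| 0.6 | 0.900 | 88% | 1.002 |
| 0.7 | 0.804 | 94% | 0.895 |

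At 0.05 the detectable effect falls by (1.124 − 1.074)/1.124 = 4% at r = 0.3, 13% at 0.5 and 28% at 0.7. The formula leaves out the small cost of chance imbalance in the covariate. On average that is a variance factor of (N − 3)/(N − 4) = 27/26 for N = 30, or about 2% on each detectable effect. It takes about two fifths of the gain at r = 0.3 and matters little from 0.5 upward.

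**4. Burden at T1.** Item counts come from section 5.2 and timing from Table 1. Demographics are left out because no count is given. The adolescent DTQ is assumed for ages 15-17 and the young adult version for 18-24.
- Not starred: AYA HOPE 13 + Knowledge 25 + PRPQ 12 + PROMIS 25 = 75 (79 for ages 18-24, whose PROMIS has 29 items).
- Starred, ages 15-17: 1 + 2 + 15 + 9 + 12 + 30 + 10 + 5 = 84 of 159 (52.8%), or 93 of 168 (55.4%) if DTQ importance ratings count as extra items.
- Starred, ages 18-24: 83 of 162 (51.2%), or 91 of 170 (53.5%).
- Starred, caregivers: 1 + 2 + 15 + 12 + 10 + 5 = 45 of 120 (37.5%).

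Adding 11 items lengthens T1 by 11/159 = 6.9% for AYA aged 15-17 and 11/120 = 9.2% for caregivers. Section 5.2 also places the preferred-role item of Control Preferences at baseline; counting it changes nothing material.

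**The case against.** **The table row is not conclusive.** The Decision-Making rows carry an extra sub-label, and only one entry survives after the scale name. A row shifted by a column would look the same whether the scale was given once or twice. Section 3.1.3 can also be read as the same assessment given twice. T2-only is the better reading, because the satisfaction and regret rows share the layout and make sense only after a decision, but it is not proven. The remedy survives either way: if T1 is already collected, only the analysis needs to change.

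**The planned test is valid.** A reader might infer that the missing baseline biases the comparison. It does not. Randomization protects a comparison of T2 scores alone, and the t test and its CI already allow for chance imbalance. Efficacy is also a preliminary, secondary aim here. This objection stands, and it limits the point to precision.

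**The gain depends on an unknown correlation.** Six weeks soon after diagnosis or relapse, with an intervention meant to shift the score, may leave r low. At 0.3 the gain is small. This stands too.

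**Some families may have decided before T1**, since enrolment is allowed up to six weeks after diagnosis. The score would still precede randomization and remain a legitimate covariate.

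**Starred scales.** A reader might infer that most of T1 is spent on scales nobody will use. The documents do not support that. The share passes half only for AYA and only without demographics: with DTQ importance ratings not counted, more than 9 demographic items (ages 15-17) or 4 (ages 18-24) would bring it below half. For caregivers it is 37.5%. Section 6 also says all measurements will be summarized. What can be said is that no comparative analysis in section 6 names a starred scale.

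**Conclusion.** The point holds as a low-cost improvement, not as an error. Self-efficacy can be measured before randomization, most plausibly is not, and is to be compared without adjustment against 10 controls. A T1 score together with ANCOVA would reduce the detectable effect by between 4% (r = 0.3) and 28% (r = 0.7), at either alpha considered.

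This rests on the T2-only reading of Table 1, which should be confirmed on the original; on an assumed correlation of 0.3 to 0.7; and on 10 and 20 evaluable families. AYA aged 18 or older may enrol alone, so the caregiver comparison may have fewer families.

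It would be too strong to say that the 11 items by themselves sharpen the comparison, since all of the gain comes through the changed analysis. The importance is minor, but the change to T1 can help only families not yet randomized.

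**What to change.** 1. Table 1: show the Decision Self-Efficacy Scale at T1 and T2 for AYA and caregivers, or confirm that it is already at T1.
2. Section 6.2: analyse T2 self-efficacy by ANCOVA with arm and T1 score, reporting the adjusted difference with its 95% CI.
3. Section 6.2: make the same adjustment for Knowledge of Clinical Trials and the PRPQ. Their T1 scores are already collected, so this adds no burden.

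The cost is 11 more REDCap items before randomization (about 7% of AYA and 9% of caregiver scale items), an amendment to the table and section 6.2, and one covariate in each model. If T1 must not grow, dropping a starred scale of similar length, such as the 12-item CFC, would offset it. That is optional and for the sponsor to weigh, because the documents give no basis for ranking the covariates.
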